PROTOCOL TITLE:

Power Training Combined with Interval Treadmill Training (PT³) to Improve Walking Activity in Cerebral Palsy

PRINCIPAL INVESTIGATOR:

[name], PT
Department of Physical Therapy
Louisiana State University Health Sciences Center - NO
Office [contact]
[contact]

Co-Investigators:

[name]
Dean's office, School of Public Health
Louisiana State University Health Sciences Center – NO
[contact]
[contact]

[name], PT
Seattle Children's Research Institute
[contact]
[contact]

[name]
Department of Urban Design and Planning
University of Washington
[contact]
[contact]

Performance Sites:

Department of Physical Therapy,
Louisiana State University Health Sciences Center
[name]
[name]

Seattle Children's Research Institute
Child Development Laboratory
[name]
[name]
[name]

Children's Hospital New Orleans
[name]
[name]

Full Protocol: Power Training Combined with Interval Treadmill Training (PT³) to Improve Walking Activity in Cerebral Palsy

Purpose

The primary purpose of this pilot study is to determine the effect of power training combined with locomotor treadmill training (PT³) on the primary outcomes of walking performance and capacity in children with CP with functional walking limitations. To identify key muscular mechanisms associated with improved walking mobility, we will examine the effects of training on muscle performance and architecture.

Rationale

Walking ability significantly deteriorates in 50% of ambulatory children with cerebral palsy (CP) beginning in childhood/adolescence. Of those who stop walking, 75% will lose the ability to walk before the age of 25, severely impacting their ability to participate in daily life. Although CP is a non-progressive neurological disorder, the sequela of musculoskeletal impairments is progressive. Strength training is routinely employed in clinical practice to counteract muscle weakness but has not been shown to improve gait speed or other measures of walking capacity. One hypothesis for the lack of improvements in ambulation is the focus of resistance training programs solely on improving muscle strength. Our prior work has documented that muscle power (product of force and velocity) is reduced by 82% as opposed to a 50% decrement in muscle strength. Muscle power is required for functional activities, such as walking, climbing stairs, and transfers, where force needs to be generated quickly in order to accomplish the intended goal. To test the hypothesis that muscle power is a key limiting factor, rather than strength, we previously conducted a randomized clinical trial comparing velocity training (a type of power training) to traditional strength training ([name], 2013). Only the velocity training intervention significantly improved gait speed and other measures of functional walking capacity. These improvements were accompanied by increased muscle power and the architectural alterations of increased fascicle length and muscle cross-sectional area. For this proposal, we hypothesize that in order to optimize ambulatory function, it is also essential to practice the task of walking, known as task-specific training. Normal walking activity in children and adolescents consist of short intervals of high step rate activity interspersed with varying intervals of low and moderate step rates. Children with CP are not able to achieve these moderate and high step rates, presumably due to the lack of muscle power generation. Therefore, it is critical that the two approaches be combined in a package of care and that the treadmill training is interval-based in order to approximate walking patterns that are developmentally appropriate and thus, stimulate muscle power generation during walking.

Specific Aims

Aim #1. Determine the immediate and retention effects of power training combined with interval treadmill training (PT³) on functional walking capacity in ambulatory children with CP.

We hypothesize that a combined impairment and task-specific approach, which targets muscle power deficits specifically, will have a significant effect on functional walking capacity as compared to an equivalent dosage of traditional impairment-based and task-specific approaches. In a randomized clinical trial, 48 ambulatory participants with CP (10 to 17yrs) will receive either PT³ or an equivalent dosage of traditional strength training combined with traditional treadmill training (comparison group) for 24 sessions, 3 times per week for 8 weeks. Outcomes will be collected at baseline and immediately post-treatment. Short and long-term retention effects will be assessed at 2 and 6 months post. Self-selected gait speed will be the primary outcome with secondary outcomes of fast gait speed, the 1-Minute Walk test and Timed-up-and-Go.

Aim #2. Quantify the effects of treatment on *in vivo* muscle architecture and muscle performance.

We hypothesize that lower extremity muscle power generation is impaired and is responsible for limitations in walking activity, and that PT³ will result in significant improvements in muscle power that will be explained partly by increases in cross-sectional area and fascicle length. Muscle architecture will be measured with ultrasound imaging, and muscle performance outcomes will be measured with isokinetic dynamometry.

Aim #3. To directly capture the effect of treatment on community-based walking activity and participation, we will use a novel combination of global position system (GPS) and accelerometry.

For this exploratory aim, we hypothesize that improved walking capacity from PT³ will enhance community-walking activity and participation captured in real-world settings. We will use coordinate data from GPS devices synchronized with StepWatch accelerometers to directly measure strides per day, stride rates, distance, duration, and location. This novel technology will allow us to better characterize walking activity outside of the clinic/laboratory setting and has far-reaching clinical implications.

Significance and Background

Gait impairments and deterioration in ambulatory children with Cerebral Palsy (CP)

Cerebral palsy (CP) is a nonprogressive developmental disorder of movement and posture that leads to activity limitation caused by damage to the immature brain before, during, or shortly after birth (Rosenbaum, 2007). CP occurs in 3.6 per 1,000 live births or 1 in 278 children, according to the Centers for Disease Control and Prevention (CDC) and is the most common physical disability originating in childhood. The CDC reports the incidence of CP is higher than childhood cancer, hearing and vision loss, spina bifida, hemophilia, fetal alcohol syndrome, and cystic fibrosis (Yeargin-Allsopp, 2008).

Although the initial brain insult is nonprogressive, CP is a lifelong disorder due to secondary musculoskeletal problems and associated activity limitations that progress into adulthood. Gait disturbances are an activity limitation that is a hallmark characteristic of CP. The progressive deterioration of walking ability begins in early adolescence and is a serious health concern. Deterioration in walking occurs in 50% of ambulatory children with CP (Jahnsen, 2004; Opheim, 2009). Of those who stop walking, 75% report walking cessation before the age of 25 while 50% report cessation before 15 years of age (Andersson & Mattsson, 2001; Murphy, 1995). Gait speed must be adequate in order for children with CP to keep up with their peers, participate in social activities, and lessen the deterioration of walking ability. Loss of independence associated with gait deterioration can lead to lower quality of life, including decreased participation in the community. Therefore, it is imperative that interventions to improve gait speed and walking ability be implemented prior to the deterioration of walking ability. Throughout the proposal, we will use the term “ambulatory children with CP” to refer to children who are categorized in Gross Motor Function Classification System (GMFCS) levels I, II, and III (Rosenbaum, 2008). These children are able to either walk independently (level I), independently but require handrails to climb stairs (level II), or with an assistive device (level III), such as a walker or crutches.

Task-specific training alone for improving walking is not sufficient

Task-specificity refers to repetitive training that specifically targets the task that one is trying to rehabilitate or improve and is based on motor learning and motor control principles related to use-dependent plasticity (Schmidt & Lee, 2011; Nudo, 2003). For example, treadmill training with and without body weight support has been advocated in order to practice the task of walking while maximizing the number of steps taken per session when compared to overground walking (Dobkin, 1999). Despite the fact that task-specificity is considered to be one of the key ingredients for effective rehabilitative therapies, task-specific training alone has not been shown to be superior to other physical therapy interventions for improving walking. This finding is consistent across multiple populations, including CP, stroke, and spinal cord injury (Damiano & DeJong, 2009; Duncan, 2011; Charalambous, 2013; Mehrholz, 2012; Mehrholz, 2014). The limitation of task-specific training for individuals with CP is the reduced capability of performing repeated practice of a task due to underlying neuromuscular deficits. Furthermore, the implementation of assistive devices, such as treadmill training with body weight support or robotic training, to make it “easier” to practice walking decreases muscle activation (van Hedel, 2006), which only further exacerbate the underlying neuromuscular deficits.

Strength training is not effective in improving walking in ambulatory children with CP

Because muscle strength has been shown to be highly correlated with gait speed and walking ability and is a significant impairment in children with CP (Damiano & Abel, 1998; Ross & Engsberg, 2007), strength training is a routinely administered intervention that is considered to be a component of standard of care for children with CP. However, results of 2 systematic literature reviews (Scianni, 2009; [name] 2016), including recent randomized controlled trials (RCTs) (Scholtes, 2012; Taylor, 2013), confirm that despite moderate increases in muscle strength, strength training is not effective in improving gait speed or other measures of walking ability in CP. A meta-analysis conducted by our research group documented a negligible effect of strength training on gait speed with an overall standardized effect size of 0.06 (p=0.51) ([name], 2016).

Power training is effective in improving walking in ambulatory children with CP

Muscle weakness has been considered one of the primary impairments contributing to activity limitations in children with CP. However, other aspects of muscle performance, such as muscle power and rate of force

[figure not shown]

Figure 1. Knee extensor strength (peak torque)(Nm) and power (watts) in CP are 64% and 18% of age-matched TD children.

these activities require force to be generated quickly in order to accomplish the intended goal. Although lower extremity muscle weakness is pervasive in CP and has been reported to be decreased by as much as 40% to 60% (Wiley & Damiano, 1998; Ross & Engsberg, 2002), we have documented that RFD and muscle power are more significantly impaired than muscle strength. We measured muscle power, RFD, and muscle strength in cohorts of ambulatory children with CP compared to an age-matched typically developing (TD) cohort. On average, peak torque, as a measure of strength, was decreased by 36% to 50%, whereas RFD and muscle power were decreased by 70% and 82%, respectively, compared to TD children ([name], 2012; [name], 2013) (Figure 1). Furthermore, lower muscle power was strongly associated with walking limitations. Our work demonstrates the importance of muscle power for walking as well as the performance of functional activities.

To examine the influence of muscle power on walking speed and functional mobility, [name] conducted an RCT to compare the effects of high-velocity training (a type of power training) versus traditional strength training of the quadriceps on muscle architecture and performance, walking speed, and functional walking mobility ([name], 2013). This trial was conducted in ambulatory children with CP (GMFCS I-III), ages 10 to 18. After 8 weeks of training (24 sessions), only children undergoing high-velocity training improved their peak power production, increased their gait speed, and distance ambulated. Participants who underwent strength training (low velocity) did not improve gait speed or distance. In addition, this study was the first to document differential muscle architectural adaptations in CP between the two types of training, thus illustrating that muscles in CP are highly plastic and are capable of responding to specificity of training stimuli. Although cross sectional area (determinant of force production) increased significantly after both strength and high-velocity training, rectus femoris fascicle (fiber) length, which is the primary architectural determinant of muscle shortening velocity, significantly increased after high-velocity training but decreased after strength training ($p=.012$). This work provides direct support for the hypothesis that deficiencies in muscle power are responsible for walking limitations in CP and can be remediated to produce clinically significant improvements in walking speed and functional walking ability. Furthermore, increases in muscle power can be explained in part by muscle architectural adaptations that are specific to resistance training at higher velocities of movement. This is a central component of power training that distinguishes it from strength training. Therefore, the underlying premise for this study is that deficits in lower extremity muscle power generation are a key limiting factor for walking in children with CP. Thus, remediating muscle power deficits will lead to improved walking abilities as evidenced by our prior work. Building on this prior work, we postulate that in order to maximize ambulation potential, participants must also practice the task of walking in order to learn how to use muscle power generation during the task of walking. We hypothesize that this combined impairment-based (power training) and task-specific (treadmill training) approach (PT3) will provide the optimal stimulus to increase walking activity and participation.

Treadmill training should be developmentally appropriate and reflect children's activity patterns rather than adult patterns

TD children and adolescents demonstrate physical activity patterns that are markedly different from adults. TD children engage in periods of intense bursts of physical activity (10-15 seconds) followed by less intense activity or rest, representing similar patterns to interval training (Armstrong, 1990; Bailey, 1995; [name], 2007). In contrast, adults typically engage in steady-state activity of a low to moderate intensity (Tudor-Locke,

development (RFD) have received far less attention, yet are important for the performance of functional activities. Whereas strength refers to the maximum amount of force or torque that a muscle can generate, muscle power refers to the ability to generate the greatest amount of force as fast as possible and is the product of force and the velocity at which the force is produced. Strength is only concerned with maximal force or torque, whereas power involves both strength and the velocity of the movement. RFD refers to the rate at which force is developed but is distinctly different from muscle power in that it can only be calculated during maximum isometric contractions whereas power can be calculated during dynamic movements. These distinctions are important because most daily activities, such as transfers, walking, and moving from a sitting to a standing position, do not require maximal muscle strength to complete the task. Rather,

2012). Despite this, treadmill training protocols for children with CP have been developed from adult protocols, which are time or endurance-based, and therefore, are not appropriate for children and adolescents.

Gait speed and stride rate (strides/min) are common temporal-spatial parameters of walking intensity (Barreira, 2012). [name] reported day-to-day walking activity using stride rate monitors ([name], 2010; [name], 2014). Activity patterns for children with CP do not approximate the same intensity levels as those of TD children. Children with CP spend the majority of their time ambulating at low intensity levels (low stride rates < 30 strides/min) and have difficulty ramping up to medium (30-60 strides/min) and high stride rates (> 60 strides/min) ([name], 2014). In addition, children with CP walked less with a significantly lower number of overall strides per day than TD youth. Therefore, we propose that treadmill training should be developmentally appropriate, reflecting the walking patterns of children rather than adults. We will address these walking limitations with "interval" treadmill training. Our interval treadmill training protocol consists of short bursts of fast walking (i.e., higher strides/min) alternating with lower to moderate intensity (i.e., lower to medium stride rates) in order to mimic age-specific walking activity that is developmentally appropriate. We also hypothesize that the inability of children with CP to ramp up to higher stride rates is due to deficits in muscle power generation. Therefore, PT3 will remediate muscle power deficits and provide the underlying muscular resources and task-specific training necessary to achieve moderate and high stride rates during walking.

Community-based as well as clinic-based outcome measures of walking activity and participation

According to the World Health Organization's International Classification of Functioning, Disability and Health (ICF), activity is defined as the execution of a task by an individual and participation refers to the involvement of an individual in a life situation. Activity and participation can be examined by capacity- and performance-based measures. Walking capacity is typically measured in the clinic and is representative of what the person is capable of doing. Walking performance, on the other hand, represents what a person actually performs in everyday life (World Health Organization, 2001). Although it is important to use valid, reliable, and standardized outcome measurements of walking capacity, such as gait speed, these outcome measures must be supplemented in order to determine overall effectiveness of an intervention, which refers to walking performance under real-world conditions. [name] et al. (2013) reported that daily walking performance measured with the accelerometry is positively correlated with participation in mobility-based life habits. Specifically, in persons with CP, reduced participation in daily activities appears related to the inability to achieve high stride rates. The proposed study will measure outcomes of both walking capacity in the clinical setting as well as walking performance out in community settings using accelerometry paired with global position system (GPS) monitoring. The StepWatch accelerometer precisely measures average strides per day and stride rate; however, such measures lack information on the location of walking. Linking StepWatch data with GPS allows measurement and characterization of the actual locations where walking activity occurs. This novel combination of measurement technology provides a method for assessing changes in performance and participation in real-world settings.

Preliminary Studies

Comparison of Power Training to Interval Treadmill Training

Preliminary data from our research team's current R21 (HD077186) investigating the effects of interval treadmill training in ambulatory children with CP ($n = 10$) showed moderate changes from pre to post-training in self-selected and fast gait speed of 0.05m/s and 0.09m/s, respectively, after 20 sessions. However, our published data from an RCT investigating high-velocity or power training in ambulatory children with CP (Section A.4) demonstrated greater changes in self-selected and fast gait speed of 0.10m/s and 0.12m/s, respectively, after 24 sessions of training ($p < 0.05$) ([name], 2013). These improvements met or exceeded the minimal clinically important difference (MCID) of 0.10m/s reported for gait speed in CP (Oeffinger, 2008).

Combined Power Training and Interval Treadmill Training (PT3)

We hypothesize that combining the two approaches (PT3) will provide the optimal stimulus to improve walking and will lead to significant gains in the primary outcome of gait speed. The PI's published power training program ([name], 2013) (i.e., high-velocity training) was conducted on an isokinetic dynamometer, which is an expensive, specialized piece of equipment that is not found in many therapy clinics. This protocol targeted the quadriceps muscle group specifically. Peak torque of the quadriceps has been shown to be highly correlated to gait speed and improved kinematics in CP (Damiano, 1995; Damiano, 2001; [name], 2012). To date, [name] (2013) is the only power training study in CP to report statistically and clinically significant improvements in gait speed and muscle power and targeted the quadriceps. It is also the only RCT to directly compare power training to strength training in CP in a controlled manner that isolated the dosing ingredients that distinguish power training from strengthening, i.e. velocity of movement and load. The power training

protocol proposed in PT3 advances the prior protocol ([name], 2013) by 1) targeting the quadriceps primarily in addition to other muscle groups that are important for gait, including the hip extensors and ankle plantarflexors; 2) using a closed kinetic chain exercise (i.e., single and bilateral leg press), which is considered to be more functional and minimizes hamstring recruitment, while adhering to same dosing guidelines; and 3) using clinically feasible, less-costly equipment in order to provide easier translation to clinical practice.

PT3 Pilot data: PT3 was conducted in hourly sessions 3 x per week for 8 weeks (24 sessions total). (See Approach for detailed protocol.) Our pilot data for PT3 documented a mean increase of 0.16m/s and 0.17m/s in self-selected and fast gait speed, respectively, after 24 sessions of PT3, resulting in a large effect size that exceeds the MCID of 0.10m/s. Distance ambulated as measured by the 1MWT increased on average by 9.8 meters, representing a large effect size that exceeds the average MCID of 7.8 meters (Hassani, 2014). These gains exceed those from either power/velocity training or interval treadmill training alone. Our pilot data also demonstrated that muscle power collected during the performance of a bilateral leg press increased by 52% on average and was accompanied by a 9% increase in rectus femoris cross-sectional area and a 15% increase in fascicle length, as measured by ultrasound imaging. Collectively, our published data (power training) and preliminary data (interval treadmill training R21 and PT3) support our hypotheses for Aims 1 and 2 and provide evidence of the feasibility of both the testing (outcome measures) and intervention protocols.

PT3 and Walking Activity and Participation in Daily Life

Walking limitations in children with CP have been documented to have a negative influence on their level of participation in daily life (Fauconnier, 2009; Lepage, 1998). To date, measures of participation have been primarily obtained via child and/or parental self-report questionnaires. Responsiveness to change and the ability to show statistical significance after an intervention has been very limited due to the subjective nature of these self-reports. In fact, out of 131 studies included in a systematic literature review of interventions for children with CP, only 5% (n=7) reported outcomes for participation and only 30% for activity (Novak, 2013). In this state of the evidence paper, Novak et al. concluded that there are no proven effective interventions for addressing participation and that research and funding should be dedicated to this important area.

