Data Analysis Plan: The primary analysis will compare differences in changes from baseline to 8 weeks post in mean response between the treatment and comparison group using a general linear model with blocking factors for intervention site and GMFCS levels as fixed factors. By employing a randomized block design, we can statistically account for any clinical heterogeneity of outcomes by study site and GMFCS levels should this occur. To gain insight into both short and long-term retention of treatment effects, response profiles over the 4 time points will be compared using a linear mixed effects model with sites and GMFCS level as blocking factors, treatment group and time as fixed effects factors, and subjects as a random factor. These models will be used for analysis of the primary and secondary response variables of Specific Aims 1 and 2. The outcomes of Specific Aim 3 will use similar analysis models but will include an additional factor to allow comparison between home and community walking activity as a separate analysis. To assess the potential impact of gender on study outcomes, gender will be included in each of the models as a fixed effect. If significant gender effects are observed, we will report both adjusted and unadjusted estimates of treatment effects to more fully reveal the role of gender. Type I error rate will be set at 0.05. The primary dataset for analysis is the intent-to-treat dataset consisting of all patients randomized to intervention. The Statistical Analysis System (SAS®), V9.4 will be used for statistical analysis using GLM and MIXED procedures.

Data Management and Fidelity: REDCap™ will be used for data management. REDCap™ is a secure application designed for building and managing databases to allow electronic data collection from multi-site studies and allows instantaneous access to data. [name] will provide oversight to extensive quality control checks incorporated into the data entry system, such as real-time validation rules (with automated data type and range checks) at the time of data entry, and tracking of critical study events, such as assessment and

intervention visits requiring physical oversight as described previously. Data management principles will be implemented to ensure the integrity, security, and confidentiality of all study-related data.

Project Timeline

Task:	Year 1			Year 2			Year 3			Year 4			Year 5		
Train Intervention/Assessment staff	X	X													
Seattle site visit by PI	X	X		X			X				X				

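### Aim 2's group comparisons are planned, but no planned analysis tests whether muscle architecture accounts for the power gain or whether power gain goes with faster walking

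*Combined protocol and SAP*

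**What the plan says.** The Purpose section states a mechanistic goal and how it will be pursued: "To identify key muscular mechanisms associated with improved walking mobility, we will examine the effects of training on muscle performance and architecture".

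Specific Aims, Aim #2 opens with a narrower objective, to quantify what treatment does to muscle architecture and performance. Its hypothesis then goes further, in two steps. The first is that "lower extremity muscle power generation is impaired and is responsible for limitations in walking activity". The second is that PT³ will raise muscle power and that this gain will be "explained partly by increases in cross-sectional area and fascicle length".

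The Data Analysis Plan names two models. The main one is to "compare differences in changes from baseline to 8 weeks post in mean response between the treatment and comparison group using a general linear model"; site and GMFCS level enter as blocking factors. For retention, "response profiles over the 4 time points will be compared using a linear mixed effects model". Gender is added as a fixed effect. The plan then says: "These models will be used for analysis of the primary and secondary response variables of Specific Aims 1 and 2".

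Power Calculations sizes Aim 2 for between-group differences in mean peak power and mean fascicle length. It gives no figure for cross-sectional area and none for any association.

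**The concern.** The hypothesis is about links between variables: architecture to power, and power to walking. The terms named for Aims 1 and 2 are treatment, time, site, GMFCS level, subject and gender. No muscle variable predicts another outcome, and no correlation, change-on-change regression or mediation model is named.

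If the plan is followed as written, the evidence that architecture accounts for power gain would be that both means moved more in the PT³ arm. The same pattern appears when the children whose fascicles lengthened are not those who gained power.

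The link to walking is weaker still. The arms differ in resistance load, volume and velocity, and also in treadmill format (interval against steady-state). Faster walking alongside greater power in the PT³ arm could therefore come from the treadmill component alone.

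At stake is the support for a stated hypothesis of Aim 2. The treatment effect on gait speed is not affected.

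**Working it through.** **1. The plan's own Aim 2 figures.** Inputs from Power Calculations: 24 per group, two-sided 0.05; fascicle length difference 1.55 cm, SD 1.61 cm; peak power difference 0.819 watts/kg, SD 0.485 watts/kg. Formula: power = Φ(d/SD × √(n/2) − 1.960).

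- Fascicle length: 1.55/1.61 = 0.963; 0.963 × √12 = 3.335; Φ(3.335 − 1.960) = 91.5%, or 90.4% with the t distribution. Stated: 90%. It reproduces.
- Peak power: 0.819/0.485 = 1.689; 1.689 × √12 = 5.850; Φ(5.850 − 1.960) is above 99.9%. Stated: 99%. Consistent.

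Both figures concern differences in means only.

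**2. Can the planned tests tell linked from unlinked changes?** Trials were simulated with 24 per arm and standardised effects of 0.963 (fascicle length) and 1.689 (peak power), 2,000 trials per setting. Only the within-arm correlation of the two changes was varied. Each change was compared between arms by a two-sample t test.

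| Within-arm correlation | Fascicle length significant | Peak power significant | Mean within-arm r recovered |
|---|---|---|---|
| 0 | 91.0% | 100% | 0.00 |
| 0.3 | 89.5% | 99.95% | 0.30 |
| 0.6 | 89.4% | 100% | 0.60 |

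The small differences in the second column are within simulation error. The between-arm tests do not respond to the correlation. The within-arm correlation, from the same data, recovers it.

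**3. What an association model could detect.** The documents give no correlation between these changes, so r = 0.3 to 0.6 is an assumed range.

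Control terms when one architecture slope is tested in the first proposed model: arm 1, site 1, GMFCS level 2 (three levels), baseline of the outcome 1, the other architecture measure 1. That makes k = 6. The second model has 5, or 6 if gender is kept as in the plan's other models.

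Fisher z, 80% power: smallest r = tanh((1.960 + 0.842)/√(n − 3 − k)).

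- n = 48: 2.802/√39 = 0.449; tanh = **0.42**.
- n = 38 (the plan's 19 per group): 2.802/√29 = 0.520; tanh = **0.48**.
- n = 36 (18 per group, since 24 × 0.75 = 18): 2.802/√27 = 0.539; tanh = 0.49.

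Without the control terms the formula gives 0.39 for n = 48 and 0.45 for n = 36, which is too favourable for an adjusted model.

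Power with k = 6, Φ(atanh(r) × √(n − 9) − 1.960):

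| Partial r | n = 48 | n = 38 |
|---|---|---|
| 0.3 | 49% | 39% |
| 0.4 | 75% | 63% |
| 0.5 | 93% | 84% |
| 0.6 | 99% | 96% |

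**The case against.** The strongest reply is that the plan does what Aim 2's headline asks. The objective is the treatment effect on architecture and performance, and the Purpose says mechanisms will be studied by examining training effects on those measures. The planned models do that, and the sample size section supports it. This stands, and a reader who inferred that Aim 2 as a whole is unserved would be wrong.

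A second reply is that a randomised differential response is itself some mechanistic evidence. In the earlier trial described in the background, cross-sectional area rose in both arms while fascicle length rose in one and fell in the other. This also stands in part: such a pattern bears on mechanism, but it does not show association within children.

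A third is that the plan's sentence on models does not say they are the only analyses. That is right: the plan is silent on association and does not exclude it. But an association analysis chosen after the data are seen, with several architecture and performance measures available, would carry little weight.

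Finally, the study calls itself a pilot and the gap touches a secondary, mechanistic clause. No primary estimate, sample size or safety matter changes, which limits how much weight the point can bear.

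**Conclusion.** The point holds in a limited form. The headline objective of Aim 2 is met by the planned comparisons. The hypothesis that architecture partly accounts for power gain, and the link from power to walking, have no planned test.

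A reader might infer that the trial cannot answer these questions. The documents do not support that: ultrasound, dynamometry and gait speed are outcome measures in the same children, on one schedule of assessments. The limit lies in the planned analysis, not the data.

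An added analysis would have 80% power only for partial correlations of about 0.42 (48 children) to 0.48 (38 children) or more. At r = 0.3 it would miss the association at least half the time, so a null result would not refute the mechanism. These figures assume about six control terms, complete pairs of visits and approximate normality. The true correlations are unknown.

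Even a clear slope would show association only. The changes are measured over the same interval, and common causes such as attendance or effort at testing could produce it.

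**What to change.** Add two models to the Data Analysis Plan, labelled exploratory, both for change from baseline to the 8-week post assessment:

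1. Change in knee-extensor peak power on the dynamometer, regressed on change in rectus femoris cross-sectional area and change in rectus femoris fascicle length.
2. Change in self-selected gait speed, regressed on change in the same peak power measure.

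Adjust both for arm, site, GMFCS level and the baseline value of the outcome. Report slopes with 95% confidence intervals, and word conclusions as association, not explanation or cause.

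Name the variables in advance. The Muscle Performance section offers power at the knee, at the ankle and on the leg press, and the Muscle Architecture section covers thigh and lower leg. State one limb rule (for example a fixed choice of limb, or the mean of both). Left open, two models become many and the benefit of pre-specification is lost.

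The cost is two extra models on data already collected. There are no new visits or participants, and the primary analysis is unchanged. The downside is wide intervals.

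If the sponsor prefers not to add them, the alternative is to withdraw the wording in Aim 2 that power gains are explained by architecture and that power is responsible for walking limits, and to report Aim 2 as treatment effects on each measure.
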